**CHARACTERIZATION OF CHANGES IN PERITONEAL CELLS GENE
EXPRESSION AFTER STANDARD VERSUS LOW PRESSURE LAPAROSCOPIC
CHOLECYSTECTOMY AND ITS CLINICAL CORRELATION.**

PROTOCOL

NCT03020641

January 27, 2017

INSTITUTION NAME: Ramón y Cajal Hospital. Madrid, Spain.

PRINCIPAL INVESTIGATORS: [name] and [name].

TITLE OF THE RESEARCH PROJECT: Characterization of changes in peritoneal cells gene expression after standard versus low pressure laparoscopic cholecystectomy and its clinical correlation.

HYPOTHESES

We hypothesized that applying a low intraperitoneal pressure of pneumoperitoneum ($\leq 8\text{mmHg}$) during laparoscopic cholecystectomy, the adverse impact on the surgical peritoneal environment (measured as gene expression of extracellular matrix adhesion and inflammatory cytokine and apoptotic index), can be minimized and probably clinical outcomes might be better.

OBJECTIVES

Primary Objective.

To characterize the changes produced in gene expression (mRNA) levels of remodelling and inflammatory markers as well as to measure apoptotic index, in peritoneal tissue, after laparoscopic cholecystectomy with low and standard pneumoperitoneum pressures ($\leq 8\text{mmHg}$ vs $\geq 12\text{mmHg}$).

The primary aim of this study is to analyse differences in those variables between both intraperitoneal pressure groups at different times: Before starting surgery (T0) and 60 minutes after surgery started.

Secondary Objectives.

To analyse within groups (high and low pressure) differences between times T0 and T1 in the same remodelling and inflammatory physiological parameters. To analyse the effect of intraperitoneal pressure in outcomes (see below).

STUDY DESIGN

This is a prospective randomized and blinded controlled trial to assess the potential adverse impact of pneumoperitoneum during laparoscopic cholecystectomy on peritoneal tissue at two different working pressures and at two different times and to correlate it with clinical outcomes as well.

STUDY GROUPS

- A. **Intervention group:** in all patients allocated to the intervention group laparoscopic cholecystectomy will be performed with pneumoperitoneum pressure (PnPr) at or below 8 mm Hg. To ease this goal deep neuromuscular block will be provided with

rocuronium till the end of surgery. Neuromuscular block will be reversed with sugammadex at a dose of 4mg/kg.

B. **Control group:** In patients allocated to this group laparoscopic cholecystectomy with abdominal pressure at 12 mm Hg or higher will be performed. In this group the level of neuromuscular block and its reversion will be done in the same way as in the intervention group.

POPULATION

Reference population: Patients undergoing elective laparoscopic cholecystectomy.

Eligibility: Patients older than 18 years, signed informed consent, undergoing laparoscopic cholecystectomy for symptomatic cholelithiasis or gallbladder polyps.

Exclusion criteria:

- Emergency surgery.
- Previous surgery at supramesocolic compartment.
- Previous peritoneal inflammatory process.
- Pregnancy or breastfeeding.
- Patient refusal to participate in the study.

RANDOMIZATION

Patients will be randomly assigned to the control or intervention group according to a simple randomization list generated by Query v.7. Allocation will be concealed till the surgical intervention date using sealed opaque numbered envelopes.

MAIN VARIABLES IN THIS STUDY ARE:

- Inflammatory peritoneal markers: (gene expression (mRNA) levels of):

- IL-1, IL-6, IL-10.
- VEGF-A “vascular endothelial growth factor A”.
- TNF α “tumor necrosis factor α ”.
- CXCL-2 “chemokine CXC ligand 2”.

- Remodeling peritoneal markers: (gene expression (mRNA) levels of):

- CTGF “connective tissue growth factor”.
- MMP-9 “matrix metalloproteinase-9”.
- PAI-1 “plasminogen activator inhibitor-1”.
- E-selectine.

- Apoptotic index.

SECONDARY VARIABLES ARE:

During the intraoperative period:

- Surgical Rating Score (SRS) to measure the working space during this laparoscopic surgery (optimal, good, acceptable, poor or very poor conditions).
- The need to change initial intraperitoneal PnPr (yes/no).
- Subjective sensation of the PnPr performed (standard or low) reported by the main surgeon (consistent vs inconsistent).
- Peak inspiratory pressure and tidal volume (mmHg).
- Total Co₂ volume administered during pneumoperitoneum (L).
- Total dose of sugammadex (mg).

During postoperative period:

- Pain measured by visual analogue scale (VAS) from 0 to 10.
- Time to start oral intake (in hours).
- Time to start ambulation (in hours).
- Long of hospital stay (in days).

STATISTICAL ANALYSIS

Biomarker data will be log-transformed before data analysis to make these variables to follow a normal distribution. Continuous variables will be expressed as mean and standard deviation. Categorical variables will be expressed as numbers and proportions. Between groups comparisons at T0 and T1 will be made by means of t-Student test. In case of non-normal distribution despite log-transformation of data we used a non-parametric alternative (U-Mann-Whitney test) instead. We will also compare within groups means differences between times T1 and T0. For this comparison we will use paired t-student test or McNemar test for normal or non-normal variable distributions respectively. Covariance analysis will be used to compare the effect of high and low pressure on parameter analysed adjusting for baseline value of the biomarker. Normality tests will be based on Kolmogorov- Smirnov. All analysis will be performed using STATA 13 (STATAcorp.2013. Stata Statistical Software: Release13. College Station, TX: StataCorpLP).

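### The primary aim covers 11 unranked markers and two unranked T1 analyses, so one nominally significant marker is weak evidence that low pressure helps

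*Combined protocol and SAP*

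**What the plan says.** **Hypothesis.** Under HYPOTHESES, low pressure is expected to reduce the adverse peritoneal impact, measured by "extracellular matrix adhesion and inflammatory cytokine and apoptotic index), can be minimized and probably clinical outcomes might be better". This is directional and is not tied to any one marker.

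**Objective.** Under OBJECTIVES, Primary Objective, the wording is descriptive: "To characterize the changes produced in gene expression (mRNA) levels of remodelling and inflammatory markers as well as to measure apoptotic index". The next paragraph turns this into a comparison of arms: "The primary aim of this study is to analyse differences in those variables between both intraperitoneal pressure groups at different times". The times are "Before starting surgery (T0) and 60 minutes after surgery started". I take the second time to be the T1 of the later sections.

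**Variables.** Under "MAIN VARIABLES IN THIS STUDY ARE" the protocol lists:
- six inflammatory mRNAs: IL-1, IL-6, IL-10, VEGF-A, TNF-alpha and CXCL-2;
- four remodelling mRNAs: CTGF, MMP-9, PAI-1 and E-selectin;
- the apoptotic index.

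**Tests.** STATISTICAL ANALYSIS first says "Between groups comparisons at T0 and T1 will be made by means of t-Student test", with a fallback: "In case of non-normal distribution despite log-transformation of data we used a non-parametric alternative (U-Mann-Whitney test) instead". It later adds "Covariance analysis will be used to compare the effect of high and low pressure on parameter analysed adjusting for baseline value of the biomarker".

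No section gives a significance level, a lead marker, a multiplicity method, a rule for how many markers must differ, an exploratory label, or an order between the two T1 analyses. No sample size is stated either.

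**The concern.** There are two gaps, and they compound.

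First, the hypothesis could be declared supported on the strength of any one of 11 markers. Testing 11 variables at a nominal level with no stated rule gives an overall chance of a false finding well above that level.

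Second, each mRNA marker has two T1 comparisons between arms. They share the T1 data but can disagree, and nothing says which result stands. The covariance sentence refers to the baseline of the biomarker, so it is also unclear whether the apoptotic index is included.

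What is at stake is how the primary result is read. The data stay usable, but a report that low pressure lowered one marker with p < 0.05 could not be taken at face value.

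**Working it through.** The plan states no error rate, sample size or power, so there is no figure of its own to reproduce.

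**1. Count the family.** 6 + 4 + 1 = 11 main variables, with IL-1 counted once, as listed. T0 precedes surgery, so T0 comparisons cannot show a pressure effect and are left out.

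**2. Assumptions, none given in the plan.** Two-sided 0.05 per test; 20 or 30 patients per arm; common inter-marker correlation 0 to 0.7; T0-T1 correlation r of 0.3 to 0.7; no true effect of pressure.

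**3. One analysis, independent markers.**
- P(at least one p < 0.05) = 1 - 0.95^11 = 0.431.
- Expected number of false positives = 11 × 0.05 = 0.55.
- P(exactly one) = 11 × 0.05 × 0.95^10 = 0.33.

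**4. Correlated markers and two analyses.** These rates come from a null simulation with 11 equicorrelated normal markers and 20,000 replicates per setting. Ranges run over 20 and 30 per arm and over r; the middle column also runs over the choice of t-test or covariance analysis.

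| Inter-marker correlation | One analysis per marker | Either T1 analysis may count |
|---|---|---|
| 0 | 0.427-0.437 | 0.512-0.613 |
| 0.3 | 0.372-0.380 | 0.454-0.547 |
| 0.5 | 0.305-0.315 | 0.369-0.465 |
| 0.7 | 0.226-0.233 | 0.280-0.351 |

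- If covariance analysis covers only the ten mRNAs, the last column runs from 0.276 to 0.600 overall.
- If either analysis counts, the error for a single marker rises from 5% to about 6.4%, 7.3% and 8.3% at r = 0.3, 0.5 and 0.7.
- The two analyses disagree on at least one of the 11 markers in 19-53% of null trials.
- Treating them as 22 independent tests would give 1 - 0.95^22 = 0.677. That overstates the risk, because they share the T1 data.

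**5. The planned switch to Mann-Whitney.** With a Kolmogorov-Smirnov check deciding the test (4,000 replicates), normal data give 0.224-0.433 for one analysis and 0.281-0.620 for either. Skewed and heavy-tailed data together give 0.221-0.424 and 0.281-0.598. The switch changes little.

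**6. What a remedy achieves.**
- Covariance analysis on one pre-named marker: simulated error 0.048-0.054.
- Bonferroni over 11: threshold 0.05/11 = 0.0045; overall error with independent tests 1 - (1 - 0.05/11)^11 = 0.049.
- Holm over 11 covariance contrasts: simulated error 0.028-0.050.

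**The case against.** - **Direction.** The hypothesis is directional, but the rates above count differences either way. Counting only one favourable direction per marker gives about 11-25% for one analysis (1 - 0.975^11 = 0.243 if independent) and about 14-37% for either. This is a fair qualification. However, the plan fixes no favourable direction for each marker, so the two-sided rate is the one that follows from it. The directional rates are still at least twice 5%.
- **Range of correlation.** Stopping at 0.7 is a choice. At 0.8 the one-analysis rate is about 0.18 and the either-analysis rate 0.23-0.29; at 0.9 they are about 0.13 and 0.17-0.21. This lowers the bottom of the range but does not bring it near 5%.
- **At least one is not exactly one.** The chance of exactly one significant marker is lower: about 33%, 20% and 11% at inter-marker correlation 0, 0.5 and 0.7. That is right. The rates here describe how often the panel yields something to report.
- **Covariance analysis is plainly the effect analysis.** Only that sentence speaks of the effect of pressure, and no text allows the better of two results to be chosen. This reading is reasonable, and under it the 28-62% range falls away. The plan does not say so, though, and the primary aim's wording (arms compared at two times) is closer to the t-test sentence. The 22-44% remains under either reading.
- **The study is descriptive.** The title and objective both speak of characterizing changes, and all 11 variables are listed in advance, so a reader can correct for their number. That softens the point. But the same document states a directional hypothesis, a randomized blinded design and hypothesis tests. If the intent is exploratory, one sentence would settle it.

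**Conclusion.** The concern holds and should be fixed. If pressure has no effect, the panel as planned would show at least one nominally significant difference in about 22-44% of trials with one analysis per marker. The figure is about 28-62% only if either T1 analysis may count. The top of the first range needs uncorrelated markers; the top of the second also needs a T0-T1 correlation of 0.7.

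All of this rests on the assumed 0.05 level, arm sizes and correlations. Sample size matters little: checks at 15 and 60 per arm gave nearly the same either-analysis rate (0.50 and 0.51 at inter-marker correlation 0.3 and r = 0.5).

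The claim is limited to nominal p-values. A very small p-value, or a consistent pattern across markers, would carry more weight.

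**What to change.** **1. Name one deciding analysis.** Use the baseline-adjusted T1 contrast for all 11 variables, and state that this includes the apoptotic index. Run covariance analysis on the log scale, or on ranks if the data are still non-normal, choosing the scale on data pooled over arms (simulated per-marker error of the rank version: 0.048-0.055). Report T0 comparisons, unadjusted T1 tests and within-group tests as descriptive.

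**2. State the status of the markers before arm-level results are seen.** Either name one lead marker, tested at 5%, and label the other ten exploratory, or label the whole panel exploratory. In both cases report all 11 estimates with confidence intervals.

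**3. Optional.** Apply Holm or Westfall-Young over all 11 only if the sponsor wants confirmatory claims on any marker.

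**Cost.** Steps 1 and 2 need wording and a few lines of code, and no new data. Step 1 gains power when T0 and T1 are correlated, because the residual SD falls by the factor √(1 - r²). For a raw difference of 0.8 SD with 20 per arm, power is 69% by t-test and 73%, 81% and 93% by covariance analysis at r = 0.3, 0.5 and 0.7. The price of step 2 is that markers labelled exploratory cannot support confirmatory claims.

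Step 3 can be expensive. The power figures below use the noncentral t with 2n - 3 degrees of freedom and effects in residual SDs:

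| Effect | 20 per arm: 0.05 → 0.0045 | 30 per arm: 0.05 → 0.0045 |
|---|---|---|
| 0.5 SD | 34% → 9% | 48% → 17% |
| 0.8 SD | 69% → 33% | 86% → 56% |
| 1 SD | 87% → 56% | 97% → 82% |

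For 80% power at 0.8 SD, the number per arm rises from 26 to 45. These losses are a worst case, because 0.0045 is Holm's smallest threshold. Later Holm thresholds relax, and Westfall-Young is less strict when markers are correlated.

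### Minor, low-cost improvement: name the Welch test and robust standard errors at T1, because simple randomisation can leave the arms unequal and the planned tests assume a common variance

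*Combined protocol and SAP*

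**What the plan says.** The RANDOMIZATION section reads: "Patients will be randomly assigned to the control or intervention group according to a simple randomization list generated by Query v.7". It gives no blocks, strata, allocation ratio or limit on imbalance. Allocation is concealed in sealed, opaque, numbered envelopes.

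Under STATISTICAL ANALYSIS:
- The comparison between arms is set out as "Between groups comparisons at T0 and T1 will be made by means of t-Student test".
- The preparatory step is aimed at normality: "Biomarker data will be log-transformed before data analysis to make these variables to follow a normal distribution".
- The only fallback is also tied to normality: "In case of non-normal distribution despite log-transformation of data we used a non-parametric alternative (U-Mann-Whitney test) instead".
- The adjusted analysis is "Covariance analysis will be used to compare the effect of high and low pressure on parameter analysed adjusting for baseline value of the biomarker".

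No unequal-variance form of the t-test, robust standard error or check of equal spread is named. The document states no sample size, significance level or SD for any biomarker.

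**The concern.** Student's t-test pools the two sample variances. With equal arms this does little harm even if the true variances differ. With unequal arms, the pooled standard error is too small when the smaller arm is the more variable one, and too large when the larger arm is. Ordinary covariance analysis has the same weakness through its single residual variance. Switching to Mann-Whitney is not a cure, because that test is not protected from unequal spread when it is read as a comparison of location.

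Simple randomisation makes unequal arms possible, and one realised split applies to the whole set of main outcomes: ten mRNA markers and the apoptotic index. If the split is poor and the arms differ in spread at T1, the p-values for the affected markers are too small or too large, and any confidence intervals are too narrow or too wide. The planned fallback would not pick this up.

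**Working it through.** **Inputs.** From the document: simple list, Student's t-test, log scale, ANCOVA on baseline. Assumed because not stated: allocation probability 1/2, two-sided 5% level, N = 40, 60 or 80, ratio of log-scale SDs at T1 of 1.5 or 2. The plan has no figure of its own to reproduce.

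**Step 1: chance of an unequal split.** With the size of one arm distributed Binomial(N, 1/2), the chance that the smaller arm holds at most 0.4N patients is 2 × P(X ≤ 0.4N).

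| N | Split | Chance, either direction | Chance that a given arm is the small one |
|---|---|---|---|
| 40 | 16:24 or worse | 26.8% | 13.4% |
| 60 | 24:36 or worse | 15.5% | 7.8% |
| 80 | 32:48 or worse | 9.3% | 4.6% |

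The last column is the relevant one for inflated error, since only one direction inflates it. At N = 100 the two-way chance is 6%, and at N = 200 it is 0.6%.

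**Step 2: error at a 60:40 split, large-sample formula.** Let f be the fraction in the more variable arm, r its SD, and 1 the SD in the other arm. Apart from a factor 1/N:
- true variance of the difference: T = r²/f + 1/(1−f)
- variance that the pooled test estimates: P = [f r² + (1−f)] × [1/f + 1/(1−f)]
- actual error: 2 × [1 − Φ(1.96 × √(P/T))]

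| r | More variable arm | T | P | P/T | Error |
|---|---|---|---|---|---|
| 1.5 | smaller (f = 0.4) | 7.29 | 6.25 | 0.857 | 7.0% |
| 2 | smaller (f = 0.4) | 11.67 | 9.17 | 0.786 | 8.2% |
| 1.5 | larger (f = 0.6) | 6.25 | 7.29 | 1.167 | 3.4% |
| 2 | larger (f = 0.6) | 9.17 | 11.67 | 1.273 | 2.7% |

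With r = 1, or with f = 0.5, P equals T and the error is 5%.

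**Step 3: simulation at the finite sample sizes.** For 16:24, 24:36 and 32:48, Student's test gives about 7 to 8.5% when the smaller arm is more variable and about 2.8 to 3.5% when the larger arm is. Welch's test gives about 5% throughout.

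**Step 4: average over all splits.** Each split's error is weighted by its binomial probability. Student's test then has 5.2%, 5.2% and 5.1% at SD ratio 1.5, and 5.6%, 5.4% and 5.3% at SD ratio 2, for N = 40, 60 and 80. Inflated and conservative draws largely cancel.

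**Step 5: covariance analysis.** At 16:24 with residual SD ratio 2, ordinary ANCOVA has simulated error of about 8.5% or 3%, depending on which arm is more variable. With HC3 standard errors it is 4.7 to 4.9% or 4.1 to 4.5%.

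**Step 6: price when variances are equal.** Simulated at about 80% power, Welch loses 0.1 percentage points at 20:20 (80.7% to 80.6%) and just under 0.5 at 16:24 (80.7% to 80.2%). HC3 is mildly conservative in small samples. With a baseline correlation of 0.5 (assumed) it loses about 2.5 points at 16:24 (79.6% to 77.0%) and 1.2 at 32:48 (81.4% to 80.2%).

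**Step 7: precision.** The average of N²/(4 n₁n₂) under simple randomisation is 1.027, 1.018 and 1.013 for N = 40, 60 and 80, an average variance penalty of 1.3 to 2.7%.

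**The case against.** The strongest reply is that three unstated things must coincide: a small trial, a poor split, and unequal spread with the larger SD in the smaller arm. The document supplies evidence for none of them.

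- **Spread.** Both arms are open-ended pressure ranges (at or below 8 mmHg, at or above 12 mmHg), so that feature does not show that one arm is more variable than the other. The hypothesis that low pressure damps the response does not show it either: a purely proportional damping shifts the log mean and leaves the log SD unchanged. If pressure has no effect at all on a marker, the arms share one distribution and Student's test holds 5% at any split. This stands. Unequal spread at T1 is possible, not shown. What remains is that a non-proportional effect could change the spread, and any confidence interval would then have the wrong coverage at an unequal split, whether or not the means differ.
- **T0.** No pressure has been applied, so the randomised arms come from one population. A reader might infer that all the between-arm p-values are at risk; the document supports this for T1 only.
- **Average error.** Step 4 shows that it stays close to nominal. This also stands. The case for acting is that the trial analyses one realised split, not the average.
- **Randomisation.** A reader might infer that the simple list is a mistake and must be regenerated. It is a valid method, and with concealed envelopes it keeps the next allocation unpredictable, which blocking partly gives up. Drift of allocation over surgical experience or laboratory runs is conceivable, but the document describes neither a learning curve nor batching.

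**Conclusion.** The point holds as a minor robustness improvement. The plan permits unequal arms and then relies at T1 on tests that assume a common variance, with no provision for its failure. The size is conditional. It assumes N of 40 to 80, a 60:40 split and log-scale SDs differing 1.5 to 2 fold, none of which the document states. In that case the true error is about 7 to 8.5% or 2.8 to 3.5% in place of 5%.

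Two stronger readings are not supported. Unequal arms alone do not distort the p-values, since a difference in spread is also needed. Nor is Student's test the only method affected, since ordinary covariance analysis shares the assumption. Conclusions from the trial are not invalid on this ground.

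**What to change.** In STATISTICAL ANALYSIS, specify the unequal-variance (Welch) t-test for the between-group comparisons of log-transformed biomarkers, and HC3 robust standard errors for the covariance analysis. Fix both before the data are seen, without a preliminary variance test. State the planned N, so that a reader can judge how likely a poor split is.

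The cost is two options in Stata. When variances are equal, Welch gives up under 0.5 percentage points of power. HC3 gives up about 1 to 2.5 points at N of 80 down to 40, under the settings in Step 6. The change can be made even if enrolment has begun.

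Optional, and only if no envelope has been opened: generate the list in randomly permuted blocks of varying size (for example 4 and 6), with block sizes known only to the person who prepares it. This keeps the arms close in number, but the last allocations in a block could be guessed if the sizes became known, and the average variance gain is only 1.3 to 2.7%.

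### Peak inspiratory pressure has no specified reading time or pre-insufflation reading, and the planned covariance analysis names only the biomarker baseline, so the arms would be compared unadjusted and with less precision than is cheaply available.

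*Combined protocol and SAP*

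**What the plan says.** The section on secondary variables, under the intraoperative period, contains the entry "Peak inspiratory pressure and tidal volume (mmHg"). It gives no reading time, no number of readings and no pre-insufflation value.

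The secondary objectives make this a between-arm comparison: "To analyse the effect of intraperitoneal pressure in outcomes (see below").

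The two time points are introduced for the tissue measurements. The primary objective reads "The primary aim of this study is to analyse differences in those variables between both intraperitoneal pressure groups at different times", and the variables it refers to are the mRNA markers and the apoptotic index. The within-group objective concerns "differences between times T0 and T1 in the same remodelling and inflammatory physiological parameters".

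The Statistical Analysis section then says "Between groups comparisons at T0 and T1 will be made by means of t-Student test", with Mann-Whitney as the fallback. It adds a covariance analysis of the effect of pressure "on parameter analysed adjusting for baseline value of the biomarker". No other adjustment appears. Allocation is "according to a simple randomization list generated by Query v.7", and no stratification is mentioned.

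**The concern.** Patients can be expected to differ in airway pressure before any gas is insufflated. Eligibility is open to adults having elective surgery for symptomatic stones or polyps, and no criterion concerns body size or lung disease. The question for this outcome is what abdominal pressure adds to each patient's own starting value. The plan handles the biomarkers on that logic, by adjusting for baseline, but does not extend it to peak inspiratory pressure. With no starting value specified, the adjustment could not be made even if the analyst wanted it.

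What is at stake is precision on one secondary outcome that should respond to the intervention. Any chance difference between the arms in starting airway pressure would also go uncorrected in the estimate.

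**Working it through.** **Inputs from the documents.** One intraoperative entry for peak pressure; T0 and T1 tied to the tissue measurements; an unadjusted t-test or Mann-Whitney test between arms; covariance analysis with the biomarker baseline as the only named covariate; simple randomisation. The documents state no sample size, power, alpha, effect size or SD, so there is no figure of the plan's own to reproduce.

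**Assumptions, none from the documents.** Two-sided alpha 0.05; equal arms; correlation ρ between the pre-insufflation and T1 peak pressure of 0.3 to 0.8; true difference 0.6 SD; 20 or 30 patients per arm.

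**Step 1: variance.** With the pre-insufflation value as covariate, the error variance is multiplied by 1 − ρ². The share removed is ρ². The unadjusted analysis needs 1/(1 − ρ²) times as many patients for the same precision.

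**Step 2: power.** The standardised difference becomes 0.6/√(1 − ρ²). It is entered in the two-sample t-test power calculation, ignoring the one degree of freedom spent on the covariate.

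| ρ | Variance removed | 1/(1 − ρ²) | 0.6/√(1 − ρ²) | Power, 20 per arm | Power, 30 per arm |
|---|---|---|---|---|---|
| unadjusted | 0% | 1.00 | 0.60 | 46% | 63% |
| 0.3 | 9% | 1.10 | 0.63 | 49% | 67% |
| 0.5 | 25% | 1.33 | 0.69 | 57% | 75% |
| 0.7 | 49% | 1.96 | 0.84 | 74% | 89% |
| 0.8 | 64% | 2.78 | 1.00 | 87% | 97% |

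**Step 3: sensitivity to the other assumptions.** At 50 per arm and 0.6 SD, power is already 84% unadjusted and rises to 93% at ρ = 0.5. If the true difference is 1.0 SD, unadjusted power is 87% at 20 per arm and 97% at 30 per arm, which leaves little to gain.

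**The case against.** The strongest reply is that the documents are silent rather than wrong. The intraoperative heading does not exclude a reading between induction and insufflation, and nothing limits the variable to one value. A reader might infer that the plan fixes a single reading during insufflation; the text does not say so. This part of the objection stands: the accurate statement is that no pre-insufflation reading is specified.

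It can also be said that the analysis wording is loose. The sentence on between-group tests is not expressly confined to biomarkers, and the covariance analysis is applied to whatever parameter is being analysed. The wording is ambiguous, but the covariate is named as the biomarker's baseline and the objectives tie T0 and T1 to the tissue markers. An unadjusted comparison of peak pressure is the natural reading.

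A third reply is that the size of the gain depends on the reviewer's assumptions. That is right. At ρ = 0.3 the gain is 3 or 4 percentage points of power, and a large effect would be detected without adjustment.

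Finally, peak pressure is hard to interpret without knowing when it was read and at what delivered volume, so baseline adjustment refines a variable that is not yet fully defined. This also stands, and it is why the reading time and the accompanying tidal volume belong in the fix.

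**Conclusion.** The point holds as a low-cost improvement to one of ten listed secondary entries. No reading time and no pre-insufflation value are specified for peak inspiratory pressure, and the planned adjustment does not reach it. The cost is lost precision: 9% to 64% of the variance is removable if ρ lies between 0.3 and 0.8. The corresponding power figures hold only for the assumed 0.6 SD and 20 or 30 per arm.

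Two stronger readings are not supported. A reader might infer that the comparison is biased; under randomisation it is not, and a chance imbalance in starting airway pressure affects an individual result rather than the validity of the test. A reader might also infer that the trial is small and so especially exposed; the documents give no sample size, so this cannot be said. The primary biomarker analysis already has baseline adjustment and is unaffected.

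**What to change.** In the list of intraoperative variables, state that peak inspiratory pressure, together with the tidal volume at that moment, is recorded just before insufflation and again 60 minutes after the start of surgery (T1). In the Statistical Analysis section, extend the covariance sentence so that T1 peak inspiratory pressure is compared between arms with its own pre-insufflation value as covariate.

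The cost is one extra set of ventilator readings per patient and one phrase in the analysis section. It needs no added procedure or staff, and the primary biomarker analysis stays as it is. The change should be made before enrolment, because no analysis can restore a starting value that was not recorded.

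### Total sugammadex in raw mg tracks body weight under the common per-kg reversal rule, so it should be reported per kg with departures from the rule, not read as a pressure outcome

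*Combined protocol and SAP*

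**What the plan says.** All references are to the combined protocol and SAP.

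- **STUDY GROUPS, A (intervention).** Deep block is kept up with "rocuronium till the end of surgery". On reversal: "Neuromuscular block will be reversed with sugammadex at a dose of 4mg/kg".
- **STUDY GROUPS, B (control).** "In this group the level of neuromuscular block and its reversion will be done in the same way as in the intervention group".
- **SECONDARY VARIABLES, intraoperative period.** The list includes "Total dose of sugammadex (mg", in milligrams and not scaled to weight. Body weight is not on either variable list.
- **OBJECTIVES, Secondary Objectives.** "To analyse the effect of intraperitoneal pressure in outcomes (see below". The primary objective already covers the main variables, so the secondary list is the only later list to which this can point.
- **STATISTICAL ANALYSIS.** "Between groups comparisons at T0 and T1 will be made by means of t-Student test", with a rank test as the fallback. The covariance analysis is described as "adjusting for baseline value of the biomarker"; no other covariate is named. No separate method is given for the secondary variables.
- **RANDOMIZATION.** Allocation uses a "simple randomization list generated by Query v.7"; no stratification is mentioned.

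The plan gives no rule for titration, repeat doses or arm-specific reversal. It does not say whether the sugammadex variable is an outcome, an adherence check or a descriptive item.

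**The concern.** A variable can carry information about pressure only if pressure can change it. Here the amount of reversal drug is set by a rule that is the same in both arms and depends only on weight, which is fixed before randomization. If the rule is followed, comparing total mg between arms means comparing body weight between arms.

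What could differ by arm is extra dosing or departure from the rule. Total mg does include those amounts, but mixes them with the much larger spread caused by differences in weight.

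The stake is interpretation of one secondary variable. An arm difference in mg might be taken as an effect of pressure on drug use when it shows only that one arm was heavier. A similar mean in both arms might be taken as evidence that pressure has no effect, when adherent dosing could not have shown one.

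**Working it through.** The plan states no sample size, SD, alpha or power, so it has no figure of its own to reproduce. The check is structural, with illustrative numbers.

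**Inputs from the documents:** 4 mg/kg in the intervention arm; the same reversal in the control arm; the variable in mg.

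**Assumptions, not in the documents:** weight roughly normal with mean 75 kg and SD 10, 15 or 20 kg; 20, 30, 50 or 100 patients per arm; 1:1 allocation; two-sided alpha 0.05.

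**Step 1: what the variable is under the rule.** For every patient, dose (mg) = 4 × weight (kg). Therefore:

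- difference in mean dose = 4 × difference in mean weight
- expected difference under randomization = 4 × 0 = 0 mg
- SD of dose = 4 × SD of weight, so 40, 60 or 80 mg

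Multiplying every value by 4 leaves a t statistic unchanged, so a t-test on mg has the same p-value as a t-test on weight.

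**Step 2: simulation.** With 20,000 simulated trials per setting, the p-values for dose and for weight agreed throughout. The rejection rate was 4.8% to 5.2% across all settings, which is the nominal 5%.

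**Step 3: size of chance differences.** 95% limits = ±1.96 × 4 × SD × √(2/n). For SD 15 kg and n = 30 per arm: 1.96 × 60 × √(2/30) = 30.4 mg.

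| n per arm | SD 10 kg | SD 15 kg | SD 20 kg |
|---|---|---|---|
| 20 | ±24.8 mg | ±37.2 mg | ±49.6 mg |
| 30 | ±20.2 mg | ±30.4 mg | ±40.5 mg |
| 50 | ±15.7 mg | ±23.5 mg | ±31.4 mg |
| 100 | ±11.1 mg | ±16.6 mg | ±22.2 mg |

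**Step 4: what raw mg would show if dosing departed from the rule.** Suppose, for arithmetic only, that a share q of one arm received an extra 2 mg/kg and nobody in the other arm did. The mean shift is 2 × q × 75 mg. With a weight SD of 15 kg and 4,000 simulated trials per setting, the power of a t-test on mg was:

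| Share q | Mean shift | Power, 30 per arm | Power, 50 per arm |
|---|---|---|---|
| 5% | 7.5 mg | 7% | 9% |
| 10% | 15 mg | 12% | 17% |
| 20% | 30 mg | 30% | 48% |

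At 30 per arm, departures in 10% of one arm shift the mean by 15 mg, about half the ±30.4 mg that chance weight imbalance can produce. On the per-kg scale adherent patients all sit at the stated value, so each departure can be seen and counted directly.

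**The case against.** The strongest reply is that the plan never says this variable will be tested between arms. The t-test is written for comparisons at T0 and T1, and the covariance analysis for biomarkers with a baseline value. A total dose has neither structure. The only statement that plainly covers it is that continuous variables are summarised by mean and SD. The intraoperative list also holds items about conduct, such as whether the initial pressure had to be changed and whether the surgeon's impression of the pressure was consistent. A record of the reversal drug given fits among these. This stands: use as a between-arm outcome is inferred from the secondary objective and not stated. But nothing labels the variable as descriptive either, and saying so is most of the remedy.

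Three stronger readings are tempting, and the documents do not support them.

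- **A reader might infer that the plan contradicts itself.** It does not. A common per-kg rule and a record of the amount given are compatible; the record can document that both arms were treated alike. Reconciliation is needed only if the dose is meant to vary.
- **A reader might infer that the variable can never carry any information on pressure.** That holds for adherent dosing. The total recorded could still differ by arm through extra doses or departures, although the plan describes none.
- **A reader might infer that weight imbalance biases the trial.** It does not. Randomization balances weight in expectation, and the simulated rejection rate is the nominal one.

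**Conclusion.** The point holds as a minor matter of how one secondary variable is defined and interpreted. Under the written rule, total mg is proportional to body weight in both arms, and a between-arm comparison of it carries no information on pressure. Where dosing departs from the rule, raw mg is an insensitive way to see it.

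The structural conclusion rests only on the study-group text and on the rule being followed. The mg limits, about ±11 to ±50 mg, rest on an assumed weight SD and an assumed sample size and serve only to show scale; the documents offer no threshold against which to judge them. The power figures rest further on an assumed extra amount given in one arm only. That a between-arm comparison is intended is an inference from the secondary objective. The primary biomarker comparison is unaffected.

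**What to change.** In the secondary variable list, replace total mg as a potential pressure outcome with a descriptive exposure and adherence variable: sugammadex per kg by arm, with the number of patients in each arm who departed from the stated rule. Total mg can still be tabulated, with a note that it is not interpreted as an effect of pressure.

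If the sponsor does intend the dose to vary between patients or arms, the study-group text and the variable list should be reconciled so that both describe the same conduct. No dose or dosing rule is proposed here.

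The cost is one line in the variable list, one fewer secondary comparison, and body weight recorded for each patient. The dose data are still collected.
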